8.2 Exclusion Criteria

1. History of any illness or any clinical condition that, in the opinion of the investigator, might confound the results of the study or pose an additional risk in administering study drug(s) to the subject. This includes, but is not limited to, the following:
 - Clinically significant liver cirrhosis with or without portal hypertension
 - Solid organ or hematological transplantation

- Alcohol or drug abuse in the past year, including, but not limited to, cannabis, cocaine, and opiates, as deemed by the investigator
 - Cancer, except for squamous cell skin cancer, basal cell skin cancer, and Stage 0 cervical carcinoma in situ (all 3 with no recurrence for the last 5 years)
2. Any clinically significant laboratory abnormalities at the Screening Visit that would interfere with the study assessments or pose an undue risk for the subject (as deemed by the investigator).
 3. Any of the following abnormal laboratory values at screening:
 - Hemoglobin <10 g/dL
 - Total bilirubin $\geq 2 \times$ upper limit of normal (ULN)
 - Aspartate transaminase (AST), alanine transaminase (ALT), gamma-glutamyl transferase (GGT), or alkaline phosphatase (ALP) $\geq 3 \times$ ULN
 - Abnormal renal function defined as glomerular filtration rate $\leq 45 \text{ mL/min/1.73 m}^2$ (calculated by the Counahan-Barratt equation)¹³
 4. An acute upper or lower respiratory infection, pulmonary exacerbation, or changes in therapy (including antibiotics) for pulmonary disease within 28 days before Day 1 (first dose of study drug).
 5. Lung infection with organisms associated with a more rapid decline in pulmonary status (including, but not limited to, *Burkholderia cenocepacia*, *Burkholderia dolosa*, and *Mycobacterium abscessus*). For subjects who have had a history of a positive culture, the investigator will apply the following criteria to establish whether the subject is free of infection with such organisms:
 - The subject has not had a respiratory tract culture positive for these organisms within the 12 months before the date of informed consent.
 - The subject has had at least 2 respiratory tract cultures negative for such organisms within the 12 months before the date of informed consent, with the first and last of these separated by at least 3 months, and the most recent one within the 6 months before the date of informed consent.
 6. An acute illness not related to CF (e.g., gastroenteritis) within 14 days before the first dose of study drug (Day 1).
 7. Ongoing or prior participation in an investigational drug study (including studies investigating ELX with or without coadministration of other study drugs) within 28 days of the Screening Visit.
 - A washout period of 5 terminal half-lives of the previous investigational study drug, or 28 days, whichever is longer, must elapse before the Screening Visit.
 - The duration of the elapsed time may be longer if required by local regulations.
 8. Use of restricted medication within specified duration before the first dose of study drug as defined in Table 9-2.

[figure not shown]
9. Pregnant and breast-feeding females. All female subjects regardless of childbearing potential status (Section 11.5.6) must have a negative pregnancy test at the Screening Visit and the Day 1 Visit.
10. The subject or a close relative of the subject is the investigator or a subinvestigator, research assistant, pharmacist, study coordinator, or other staff directly involved with the conduct of the study at that site.

9 STUDY IMPLEMENTATION

9.1 Study Design

This is a Phase 3b, randomized, double-blind, placebo-controlled, parallel-group, multicenter study in CF subjects aged 6 through 11 years who are heterozygous for the *F508del* mutation and a minimal function mutation (F/MF) (Figure 9-1).

Figure 9-1 VX19-445-116 Study Design

ELX: elexacaftor; IVA: ivacaftor; N: number of subjects; TEZ: tezacaftor

^a The Safety Follow-up Visit is scheduled to occur 28 days (± 7 days) after the last dose.

^b Subjects who complete the visits in the Treatment Period, regardless of whether they are on a treatment interruption, will be offered the opportunity to enroll in an optional open-label extension safety study evaluating ELX/TEZ/IVA. The Safety Follow-up Visit is not required for subjects who complete the Week 24 Visit and have enrolled in an open-label study within 28 days after the last dose of study drug.

Approximately 108 subjects will be randomized (1:1) to the ELX/TEZ/IVA group or the placebo group. The planned dosages to be evaluated are shown in Table 9-1.

Table 9-1 Treatment Period Groups and Dosages

Treatment Group	ELX Dosage	TEZ Dosage	IVA Dosage
Weight at Screening Visit			
ELX/TEZ/IVA			
<30 kg	100 mg qd	50 mg qd	75 mg q12h
≥ 30 kg	200 mg qd	100 mg qd	150 mg q12h
Placebo	0 mg	0 mg	0 mg

ELX: elexacaftor; IVA: ivacaftor; q12h: every 12 hours; qd: once daily; TEZ: tezacaftor

Note: Study drug administration is described in Section 9.6.

Randomization will be stratified by LCI_{2.5} determined at the Screening Visit (<10 versus ≥10) and weight at the Screening Visit (<30 kg versus ≥30 kg).

9.1.1 Screening

Screening Visit assessments are listed in Table 3-1.

Screening will occur within 28 days before administration of study drug. The investigator (or an appropriate authorized designee) will obtain informed consent and assent, if applicable, for each subject before any study procedure takes place.

To prepare for study participation, subjects will be instructed on the study restrictions (Section 9.4 and concomitant medications (Section 9.5).

9.1.1.1 Repetition of Screening Assessment(s)

Screening assessments may be repeated once to establish study eligibility. If repeat values of the individual assessment(s) are within the eligibility criteria and completed within the screening window, then the subject is eligible for the study.

9.1.1.2 Rescreening

Subjects may be rescreened once. If a subject is rescreened, the subject will provide re-consent and assent (as applicable), and all screening assessments will be repeated, except for:

- *CFTR* genotyping
- Ophthalmologic examination (if performed within 3 months before the date of informed consent)

If a subject is rescreened, a new screening window will begin when the first rescreening assessment has been initiated.

9.1.1.3 Extension of Screening Period Window

A subject may have the Screening Period window extended by 2 weeks for the following reasons:

- Repetition of the Screening Period assessments (Section 9.1.1.1)
- Unexpected operational or logistic delays, or to meet the eligibility criteria
- Scheduling of ophthalmologic examination (Section 11.5.5)

9.1.2 Treatment Period

The Treatment Period will last approximately 24 weeks. Study drug administration details are provided in Section 9.6.

Subjects who prematurely discontinue study drug treatment will remain in the study from the time of discontinuation of study drug treatment through the last scheduled study visit and complete the assessments for all study visits, as described in Section 9.1.4.

9.1.3 Follow-up

The Safety Follow-up Visit is scheduled to occur 28 (± 7) days after the last dose of study drug for subjects who complete study drug dosing and for subjects who prematurely discontinue study drug dosing, as described in Section 9.1.4.

An open-label extension safety study will be available for subjects who complete the last treatment period visit and are eligible. The Safety Follow-up Visit is not required for subjects who complete the Week 24 Visit and enroll in the optional open-label extension safety study within 28 days after the last dose of study drug.

9.1.4 Early Termination of Treatment

If a subject prematurely discontinues study drug treatment, an Early Termination of Treatment (ETT) Visit should be scheduled as soon as possible after the decision to discontinue treatment. Subjects who prematurely discontinue treatment will also be required to complete the Safety Follow-up Visit (Table 3-2) if applicable (Section 9.1.3).

If a subject withdraws from the study and also withdraws consent or assent, no further assessments will be performed. Vertex may retain and continue to use any data and samples collected before such withdrawal of consent or assent.

If the ETT Visit occurs 3 weeks or later following the last dose of study drug, then the ETT Visit will replace the Safety Follow-up Visit, and a separate Safety Follow-up Visit will not be required.

Subjects who prematurely discontinue study drug treatment will continue to complete all scheduled study visits for assessments following completion of the ETT Visit, as detailed in Table 3-2.

Subjects who prematurely discontinue treatment are not eligible to enroll in the optional open-label extension safety study.

9.1.5 Lost to Follow-up

A subject will be considered lost to follow-up if both of the following occur:

- The subject misses 2 consecutive study visits (telephone contact and/or clinic visit) and is subsequently unable to be contacted by telephone (3 documented attempts by telephone within 2 weeks following the second missed visit)
- The subject does not respond within 2 weeks to a registered letter sent after the 3 attempted telephone contacts.

9.1.6 Completion of Study Participation

Completion of study participation for each individual subject is defined as 1 of the following:

- For subjects who complete the Treatment Period and enter an open-label extension safety study within 28 days of the Week 24 Visit: the Week 24 Visit
- For subjects who complete the Treatment Period and do not enter an open-label extension safety study within 28 days of the Week 24 Visit: the Safety Follow-up Visit
- For subjects who prematurely discontinue study drug treatment but do not withdraw consent (and assent, as applicable): the latest of the Week 24 Visit, ETT Visit, or Safety Follow-up Visit (if required)
- For subjects who withdraw consent or assent: date of withdrawal of consent or assent, whichever is earlier (Section 9.9)

If subjects are lost to follow-up (Section 9.1.5) the date of completion of study participation will be defined as the date of the last contact the subject had with the site.

The end of study is defined in Section 13.2.8.

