ELX: elxacaftor; IVA: ivacaftor; N: number of subjects; TEZ: tezacaftor

Note: Subjects will be randomized 1:1 to receive ELX/TEZ/IVA or placebo

^a The Safety Follow-up Visit is scheduled to occur 28 days (\pm 7 days) after the last dose.

^b Subjects who complete the visits in the Treatment Period, regardless of whether they are on a treatment interruption, will be offered the opportunity to enroll in an optional open-label extension safety study evaluating ELX/TEZ/IVA. The Safety Follow-up Visit is not required for subjects who complete the Week 24 Visit and have enrolled in an open-label study within 28 days after the last dose of study drug.

Subjects will receive ELX/TEZ/IVA or placebo at the doses in Table 2-1 based on their weight at the Screening Visit.

Table 2-1 Treatment Period Groups and Dosages

Treatment Group	Weight at Screening Visit	ELX Dosage	TEZ Dosage	IVA Dosage
ELX/TEZ/IVA				
	<30 kg	100 mg qd	50 mg qd	75 mg q12h
	\geq 30 kg	200 mg qd	100 mg qd	150 mg q12h
Placebo				
		0 mg	0 mg	0 mg

ELX: elxacaftor; IVA: ivacaftor; q12h: every 12 hours; qd: once daily; TEZ: tezacaftor

Randomization will be stratified by LCI_{2.5} determined at the Screening Visit (<10 versus \geq 10) and weight at the Screening Visit (<30 kg versus \geq 30 kg).

Assessments Efficacy Assessments:

Multiple-breath washout (MBW), [REDACTED]

PD Assessment:

Sweat chloride

Safety Assessments:

AEs, clinical laboratory assessments, ECGs, vital signs, pulse oximetry, physical examinations, and ophthalmologic examinations

[REDACTED]

Statistical Analyses The primary efficacy endpoint is the absolute change in $LCI_{2.5}$ from baseline through Week 24. The primary null hypothesis to be tested is that the mean absolute change in $LCI_{2.5}$ from baseline through Week 24 is the same for the 2 treatment groups, ELX/TEZ/IVA and placebo. The null hypothesis will be tested at a 2-sided significance level of 0.05.

Assuming a within-group standard deviation (SD) of 1.5 and a 10% dropout rate through Week 24, a sample size of 54 subjects in each treatment group (108 subjects total) will have approximately 90% power to detect a difference of -1.0 for the mean absolute change in $LCI_{2.5}$ from baseline through Week 24 between the 2 treatment groups, based on a 2-sided 2-sample t-test at a significant level of 0.05.

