Event/ Assessment ^a	Day 1 ^b	Day 3 ± 1 day	Day 15 ± 3 days	Week 4 ± 5 days	Week 8 ± 5 days	Week 12 ± 5 days	Week 16 ± 5 days	Week 20 ± 5 days	Week 24 ± 5 days	ETT Visit	Safety Follow-up ^c 28 (± 7) Days After Last Dose of Study Drug	Comments
Clinic Visit	X		X	X	X		X		X	X	X	
Telephone contact		X				X		X				Assess subject's status, any AEs, concomitant medications, treatments, and procedures.
Inclusion/ exclusion criteria review	X											Section 8
Randomization	X											Randomization may occur on either Day - 1 or Day 1, after all eligibility criteria are confirmed.
Safety and Efficacy Assessments												
Ophthalmologic examination									X at or up to 4 weeks before	X		Section 11.5.5
Height and weight	X		X	X	X		X		X	X	X	Measured before study drug dosing with shoes off

^a All assessments will be performed before dosing unless noted otherwise.

^b To enter the Treatment Period, conditions for entry must be satisfied.

^c The Safety Follow-up Visit is not required for subjects who complete the Week 24 Visit and enroll in an optional open-label extension safety study within 28 days after the last dose of study drug (Section 9.1.3).

Table 3-2 Study VX19-445-116: Treatment Period and Safety Follow-up Visit

Event/ Assessment ^a	Day 1 ^b	Day 3 ± 1 day	Day 15 ± 3 days	Week 4 ± 5 days	Week 8 ± 5 days	Week 12 ± 5 days	Week 16 ± 5 days	Week 20 ± 5 days	Week 24 ± 5 days	ETT Visit	Safety Follow-up ^c 28 (± 7) Days After Last Dose of Study Drug	Comments
Vital signs and pulse oximetry	X		X	X	X		X		X	X	X	Performed after subject has been at rest for at least 5 minutes (Section 11.5.3)
Physical examination	X								X	X		Symptom directed physical examinations may be performed at any time if deemed necessary by the investigator (Section 11.5.3)
Standard 12-lead ECG	X				X		X		X	X	X	Performed prior to any procedure that may affect heart rate (e.g., blood draws) and after subject has been at rest for at least 5 minutes (Section 11.5.4)

Table 3-2 Study VX19-445-116: Treatment Period and Safety Follow-up Visit

Event/ Assessment ^a	Day 1 ^b	Day 3 ± 1 day	Day 15 ± 3 days	Week 4 ± 5 days	Week 8 ± 5 days	Week 12 ± 5 days	Week 16 ± 5 days	Week 20 ± 5 days	Week 24 ± 5 days	ETT Visit	Safety Follow-up ^c 28 (± 7) Days After Last Dose of Study Drug	Comments
Sweat chloride	X		X	X	X		X		X	X		
Multiple-breath washout	X		X	X	X		X		X	X		Performed in multiple replicates, pre-bronchodilator, before the AM dose, and before spirometry assessment (Section 11.3.1).

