12.3 Statistical Analysis

12.3.1 General Considerations

Continuous variables will be summarized using the following descriptive summary statistics: number of subjects (n), mean, SD, median, minimum value (min), and maximum value (max).

Categorical variables will be summarized using counts and percentages.

Treatment-emergent (TE) period will include the time from the first dose of study drug in the Treatment Period (ELX/TEZ/IVA or placebo) through 28 days after the last dose or the completion of study participation date (as defined in Section 9.1.6), whichever occurs first.

Baseline unless otherwise specified, will be defined as the most recent non-missing measurement (scheduled or unscheduled) collected before the first dose of study drug. For ECG, baseline will be defined as the most recent pretreatment measurement, or the average of triplicate measurements if the most recent pretreatment measurement is obtained in triplicate, before the first dose of study drug.

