9 STATISTICAL ANALYSIS

9.1 General Considerations

Continuous variables will be summarized using the following descriptive summary statistics: the number of subjects (n), mean, SD, median, minimum value (min), and maximum value (max).

Categorical variables will be summarized using counts and percentages.

Baseline value, unless otherwise specified, will be defined as the most recent non-missing measurement (scheduled or unscheduled) collected before the first dose of study drug in the Treatment Period.

Absolute change from baseline will be calculated as post-baseline value – baseline value.

Relative change from baseline will be calculated as (post-baseline value – baseline value)/baseline value.

Treatment-emergent (TE) Period will include the time from the first dose date of study drug to 28 days after the last dose of the study drug or to the date of completion of study participation, whichever occurs first.

Unscheduled visits: Unscheduled visit measurements will be included in analysis as follows:

- 1) In scheduled visit windows per specified visit windowing rules
- 2) In the derivation of baseline and last on-treatment measurements
- 3) In the derivation of maximum and minimum values during TE period, and maximum and minimum change from baseline values during TE period for safety analyses
- 4) In individual subject data listings as appropriate

Visit windowing rules: The analysis visit windows for protocol-defined visits are provided in [Appendix A](#).

Incomplete/missing data will not be imputed, unless specified otherwise.

Outliers: No formal statistical analyses will be performed to detect or remedy the presence of statistical outliers, unless specified otherwise.

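### Protocol 9.1.6 counts the 28-day rollover window from the Week 24 Visit while every other section counts it from last dose, so the treatment-emergent period can be cut back to Week 24 for a subject who still owes the Safety Follow-up Visit

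*Protocol*

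**What the plan says.** Two rules use a 28-day rollover window, and they start it on different days.

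- **Completion of participation (Protocol 9.1.6, first bullet).** The clock starts at Week 24, and completion is set there for subjects who "enter an open-label extension safety study within 28 days of the Week 24 Visit: the Week 24 Visit". The second bullet uses the same clock and sends everyone else to the Safety Follow-up Visit.
- **Waiver of the Safety Follow-up Visit.** The clock starts at last dose. Protocol 9.1.3 waives the visit for subjects who complete Week 24 and "enroll in the optional open-label extension safety study within 28 days after the last dose of study drug". Table 3-2 footnote c says the same ("enroll in an optional open-label extension safety study within 28 days after the last dose of study drug"), as does footnote b to the design figure in the Synopsis ("have enrolled in an open-label study within 28 days after the last dose of study drug"), in Protocol 9.1 and in SAP 7.1.

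Footnote b also offers rollover to subjects who complete the visits "regardless of whether they are on a treatment interruption", so a gap between last dose and Week 24 is foreseen.

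The completion date feeds the analysis. Protocol 12.3.1 runs the treatment-emergent (TE) period "through 28 days after the last dose or the completion of study participation date (as defined in Section 9.1.6), whichever occurs first". SAP 9.1 gives the same end: "28 days after the last dose of the study drug or to the date of completion of study participation, whichever occurs first".

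**The concern.** No text reconciles the two clocks. A subject can be late by the last-dose clock, and so owe the follow-up visit, while being in time by the Week 24 clock, and so have participation closed at Week 24. Because the TE period stops at completion, it then stops before the off-drug follow-up that the protocol still requires.

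What is at stake is classification more than collection. Entry in a conflict case cannot come before last dose + 29, so a follow-up visit on last dose + 21 to + 28 always precedes it and its adverse events are collected. Adverse events are queried at every visit (Protocol 13.1.1.3), and clinically significant laboratory and ECG findings have their own reporting rules (11.5.2, 11.5.4). Once the subject enters the extension, however, the completion date reverts to Week 24. The consequences are:

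- An event that began or worsened after Week 24 becomes post-treatment. It stays in the listings but leaves the TEAE tables (Protocol 12.3.4.1, SAP 9.4.1). The rule works by date, so a serious event would also leave the serious-TEAE tables. Expedited SAE reporting runs through the Safety Follow-up Visit (13.1.2.2) and is not affected.
- A medication first started in those days leaves the concomitant-medication tables (SAP 9.2.4, Table 12-2).
- The laboratory, ECG and vital-sign threshold counts and the oximetry shift table are also tied to the TE period (SAP 9.4.2 to 9.4.5). By-visit summaries are less clear, because Appendix A gives most of these assessments a nominal Safety Follow-up visit.

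Holds called for by the protocol include those for transaminase elevation and severe or serious rash (9.8.1, 9.8.2), and these are the two adverse events of special interest (SAP 9.4.1.1). The subjects exposed may therefore include some whose off-drug follow-up matters.

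**Working it through.** The check is date logic; the plan gives no figure of its own to reproduce.

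**Inputs**

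- g = days from last dose to the Week 24 Visit. For a fully dosed subject g = 1 (last dose the evening before, Protocol 9.6.1). A hold just over 72 hours (9.8) gives about g = 4. Larger values are assumptions.
- e = days from Week 24 to extension entry. Assumed range 0 to 28, which is 29 possible entry days.
- v = days from last dose to the Safety Follow-up Visit: 28 ± 7, so 21 to 35 (9.1.3).
- Week 24 target day: 169 (SAP Appendix A).

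**When the rules conflict.** The visit is owed if g + e > 28. Participation is closed at Week 24 if e ≤ 28. Both hold for e from max(0, 29 − g) to 28. The opposite mismatch needs g + e ≤ 28 with e > 28, which is impossible for g ≥ 0, so the error runs one way only.

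**TE days lost in a conflict case.** The end of the TE period is counted here in days after last dose.

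- As written: min(28, g).
- With completion at the later of Week 24 and the follow-up visit: min(28, max(g, v)).
- Loss for g < 28: max(0, min(28, v) − g). For g ≥ 28 the loss is zero, because the 28-day cap has already been reached by Week 24.

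| g | Conflicting e | Entry days in conflict, of 29 | Days lost, v = 21 | Days lost, v ≥ 28 |
|---|---|---|---|---|
| 1 | 28 | 1 | 20 | 27 |
| 4 | 25–28 | 4 | 17 | 24 |
| 7 | 22–28 | 7 | 14 | 21 |
| 14 | 15–28 | 14 | 7 | 14 |
| 20 | 9–28 | 20 | 1 | 8 |
| 24 | 5–28 | 24 | 0 | 4 |
| 27 | 2–28 | 27 | 0 | 1 |
| ≥ 29 | 0–28 | 29 | 0 | 0 |

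A short hold loses more days but conflicts on fewer entry dates. A hold is not strictly necessary: a fully dosed subject who enters exactly 28 days after Week 24 is 29 days from last dose.

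**Worked case.** Last dose Day 155, Week 24 Day 169 (g = 14), entry Day 190 (e = 21).

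- From last dose: 190 − 155 = 35 > 28, so the visit is owed, between Day 155 + 21 = 176 and Day 155 + 35 = 190.
- From Week 24: 190 − 169 = 21 ≤ 28, so completion is Day 169.
- TE end as written: min(155 + 28, 169) = min(183, 169) = Day 169.
- TE end with one clock: Day 176 (visit at its earliest) to Day 183 (visit at last dose + 28 or later).
- Loss: 176 − 169 = 7 to 183 − 169 = 14 days.

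**The case against.** The strongest reply is that the rules serve different purposes. One says when a visit may be skipped, and the other assigns a hand-over date. A single hand-over date for everyone who rolls over is a defensible convention, and it already ends the TE period at Week 24 for subjects whose visit is properly waived, at a cost of up to 28 − 1 = 27 days for a fully dosed subject. The conflict also needs a coincidence of dates: for a fully dosed subject it arises on one entry day of 29, and otherwise it takes an unresolved hold plus delayed entry. Subjects who discontinue treatment cannot enter the extension (9.1.4) and have their own completion rule. Relabelled events remain in the listings, and no safety conclusion has been shown to change.

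The points about rarity and limited effect stand, and they are why this is minor. The convention argument does not remove the conflict. For a waived subject, ending at Week 24 is intended and no further parent-study visit is due. Here the protocol still requires the visit, then dates participation as if it were not due. The two purposes are linked, because the completion date decides what counts as treatment-emergent.

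It is also fair that the extension protocol is not among the documents, so its handling of events around entry cannot be checked.

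**Conclusion.** The rule in 9.1.6 is wrong as written, at minor severity. It conflicts with every other statement of the rollover window. In the conflict cases with the last dose less than 28 days before Week 24, it can shorten the TE period by up to 27 days: 7 to 14 days for a 14-day hold, 1 to 8 for a 20-day hold, and none once the gap reaches 28 days.

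These day counts follow from the documents' rules. The hold lengths and entry dates are assumptions. The number of subjects affected is not given and is expected to be small. The LCI and sweat chloride analyses and SAE reporting are unaffected. Ending the TE period at Week 24 for subjects whose visit is waived is intended and is not part of this point.

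**What to change.** Change two bullets in Protocol 9.1.6.

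1. In the first and second bullets, start the 28-day window at the last dose of study drug, as 9.1.3 does.
2. In the second bullet, set completion at the later of the Week 24 Visit and the Safety Follow-up Visit, where that visit is required. The later-of form is needed because for g ≥ 22 the follow-up window opens before Week 24 (last dose + 21 is at least one day earlier). The third bullet, for subjects who discontinue treatment, already takes the latest of its visits.

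Protocol 9.1.3, the footnotes and the SAP need no change, since the SAP takes the completion date as given.

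The change adds no visit or procedure. For a few subjects, parent-study collection of adverse events and medications may run past extension entry by at most 35 − 29 = 6 days (entry no earlier than last dose + 29, visit no later than last dose + 35). How the extension would handle that overlap cannot be checked here. Open-label dosing cannot enter the TE period, which stays capped at last dose + 28. A follow-up visit on last dose + 29 to + 35 remains outside the TE period under either wording.
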